Steering Committee	
Academic Centre for General Practice, KU Leuven [name] [name], [name] [name] [name] [name] Belgium
 
Department of Family Medicine and Primary Health Care, Ghent University [name] [name] [name] [name]
 
Department of General Practice, U Antwerp [name], [name]

[name]
[name]
[name]

Vakgroep Huisartsgeneeskunde, VUB
[name] [name]
[name]
[name]

UR Soins primaires et Santé, Liège Université
[name] [name], [name]
[name]
[name]

Département de Médecine générale, ULB
[name]. [name], [name]
[name]
[name]
[name]

KCE, Federaal kenniscentrum voor de gezondheidszorg
[name] or representative
[name]
[name]

Clinical Trial Unit (CTC), UZ Leuven
UZ Leuven
[name]
[name]

Leuven Biostatistics and Statistical Bioinformatics Centre, KU Leuven
[name]
[name]
[name]

Algemeen Medisch Labo (AML)
[name]
[contact]
[name]
[name]

Clinical Pharmacology – Department of Pharmacology, UGent
[name] [name]
[contact]
[name]
[name]

Trefpunt Zelfhulp
[contact]

	
[name] [name]
 
Patient involvement [name] and [name]

--	---

TRIAL SUMMARY

Trial Title	The effectiveness of a blended care program for the discontinuation of benzodiazepines use for sleeping problems in primary care: a clustered randomized trial.	
Short Title	Blended care for the discontinuation of benzodiazepine use: Big Bird trial	
Trial Design	Cluster randomized controlled trial	
Trial Participants	Primary care patients aged 18 and older receiving prescriptions for (z-) benzodiazepines ((z-)BZD) for daily use in the last 6 months for a primary indication of sleeping problems.	
Planned Sample Size	120 general practitioners randomised, each recruiting 10 patients, totalling 1200 patients	
Treatment duration	1-6 months	
Follow up duration	12 months	
Planned Trial Period	42 months	
	Objectives	Endpoints
Primary	To compare the long-term effect of a blended care approach (interactive learning e-tool and face-to-face contacts with general practitioner) versus usual care on the discontinuation of (z-)BZD	Proportion of patients that discontinued (z-)BZD use at 12 months assessed by toxicological screening
Secondary	To compare the short-term effect of a blended care approach (interactive learning e-tool and face-to-face contacts with GP) versus usual care on the discontinuation of (z-)BZD	Proportion of patients that discontinued (z-)BZD use at 6 months assessed by toxicological screening
	To compare the effect of a blended care approach (interactive learning e-tool and face-to-face contacts with GP) versus usual care on the quality of life	EQ5D-3L assessed at week 6, 12, 26 and 52

	To compare the effect of a blended care approach (interactive learning e-tool and face-to-face contacts with GP) versus usual care on self-reported discontinuation of (z-)BZD use	Proportion of patients with self-reported discontinuation of (z-)BZD use assessed at week 6, 12, 26 and 52
	To compare the effect of a blended care approach (interactive learning e-tool and face-to-face contacts with GP) versus usual care on the number of defined daily doses (DDD) of benzodiazepines prescribed	The number of DDD of (z-)BZD prescribed in the preceding interval assessed at week 6,12,26 and 52
Intervention(s)	
In the control arm, patients will receive ‘usual care’ left at the discretion of the treating GP. They are expected to follow the Belgian guidelines as described in the most recent online version of “Anxiety, stress and sleeping problems A toolbox for general practitioners.” or “Sleeping pills and sedatives. How to assist your patients in the search for other solutions?” which are available both in French and Dutch.
 
The recommended approach proposed in this toolbox typically involves education of the patient about the harmful effects of chronic (z-)BZD and the alternatives, and the advice to discontinue (z-)BZD use.
 
A stepped approach is recommended. In a first instance a minimal intervention strategy such as a discontinuation letter or a short advice is applied. In case the minimal intervention failed or in case the GP judges the chance of a successful minimal intervention to be unlikely, a brief intervention is recommended which may span one or more consults. During such intervention, the GP will –based on the principles of motivational interviewing- assess the patient’s readiness for change and match the appropriate intervention.
 
A (z-)BZD tapering scheme will be developed which typically consists of a 10–20% reduction in the daily dose of the (z-)BZD every 2–4 weeks. To facilitate withdrawal a switch from a (z-)BZD with a short half-life to diazepam may be considered.
 
In the intervention arm an interactive e-learning programme delivered through a secured web-based platform for patients and general practitioners (GP) is blended with face-to-face contacts between the involved GP and patient. The e-tool provides psycho-education about sleep and sleeping disorders, sleeping medication and its associated risks, non-pharmacological alternatives and tapering of (z-)BZD. Furthermore, a sleeping diary allows patients to enter information about their sleeping habits, sleep hygiene, coping techniques, triggers and facilitators. The purpose of this e- tool is to motivate patients to discontinue the use of (z-)BZD, to adapt alternative remedies
	

and to support them in this process. The e-tool features cognitive behavioural techniques enhancing the self-management of the patient. In a first contact, patients will receive access to the interactive e-learning module and be requested to pass through the educational sessions at their own pace. In the face-to-face contacts the patients' sleeping diary, insights and experiences will be discussed and the GP will assess the patients' readiness to discontinue (z-)BZD use. Participating GPs will have access to the interactive parts of the module of their patients, making it possible to discuss issues with the patients during the face-to-face consultations.

In **both arms**, once the patient is willing to withdraw, a tailored gradual taper of the (z-)BZD will be agreed upon, which typically consists of a 10–20% reduction in the daily dose of the (z-)BZD every 2–4 weeks. To facilitate withdrawal a switch from a (z-)BZD with a short half-life to diazepam may be considered.

Follow-up appointments will be scheduled depending on the needs of the patient until the end of dose reduction. During these follow-up visits progression and (z-)BZD withdrawal-related problems will be discussed.

ROLE OF STUDY SPONSOR AND FUNDER

The Belgian Health Care Knowledge Centre, as mentioned in KEY TRIAL CONTACT, provides funding for this trial.

UZ/KU Leuven, as mentioned in KEY TRIAL CONTACT, acts as sponsor of the Study, as defined in the Law of 2004, and shall assume all responsibilities and liabilities in connection therewith and procure the mandatory liability insurance coverage in accordance with the Law of 2004. **UZ/KU Leuven** shall ensure that it shall be mentioned in the Protocol, the Informed Consent Forms and in other relevant communication with the Study Subjects or the Regulatory Authorities as sponsor of the Study. **UZ/KU Leuven** acknowledges and agrees for the avoidance of doubt that KCE shall under no circumstances be considered as sponsor of the Study or assume any responsibilities or liabilities in connection therewith, and **UZ/KU Leuven** shall make no representations whatsoever in this respect.

ROLES AND RESPONSIBILITIES OF TRIAL MANAGEMENT COMMITTEES

Trial Steering Committee (TSC)

The TSC is composed of the following participants:

- UZ Leuven Clinical Trial Centre
- Chief Investigator: [name]
- Academic Centre for Primary Care (ACHG), KU Leuven: [name]
- Department of General Practice and Primary HealthCare, UGent: [name]
- Department of General Practice, U Antwerp: [name], [name]
- Department of General Practice, VUB: [name]
- UR Soins primaires et Santé, LIEGE Université: [name], [name]
- ULB: [name]
- Leuven Biostatistics and Statistical Bioinformatics Centre, KU Leuven
- Clinical Pharmacology – Department of Pharmacology, UGent: [name]
- Patient representatives

KCE shall have the right (but not the obligation) to be present at each TSC meeting (more details can be found in the research agreement template).

Role of TSC:

- The TSC shall oversee the performance of the study and discuss important topics in relation thereto.
- The TSC shall monitor trial progress, conduct and advise on scientific credibility.
- The TSC will consider and act, as appropriate, and ultimately carries the responsibility for deciding whether a trial needs to be stopped on grounds of safety or efficacy.
- The TSC shall meet regularly and send reports to the sponsor.

Meetings of TSC:

The TSC will meet on average 3 times per year or as necessary when adapted to the stage of the trial (set-up, conduct, analysis).

Trial Management Group (TMG)

[figure not shown]
The day-to-day management of the study will be performed by the TMG which is distinct from the TSC and consists of the chief investigator and the trial coordinators.

LIST OF ABBREVIATIONS

ABBREVIATION	DEFINITION
AE	Adverse Event
AR	Adverse Reaction
CBT	Cognitive Behavioural Therapy
CI	Chief Investigator
CME	Continued medical education
DSUR	Development Safety Update Report
eCRF	Electronic Case Report Form
EC	Ethics Committee
EHR	Electronic Health Record
EudraCT	European Clinical Trials Database
GCP	Good Clinical Practice
GP	General Practitioner
ICF	Informed Consent Form
ICH	International Conference on Harmonisation of technical requirements for registration of pharmaceuticals for human use.
IMP	Investigational Medicinal Product
ISF	Investigator Site File
ISRCTN	International Standard Randomised Controlled Trials
KCE	Belgian Healthcare Knowledge Centre
MA	Marketing Authorisation
PI	Principal Investigator
RCT	Randomised Control Trial
REC	Research Ethic Committee
SAE	Serious Adverse Event
SAR	Serious Adverse Reaction
SOP	Standard Operating Procedure
SmPC	Summary of Product Characteristics
SUSAR	Suspected Unexpected Serious Adverse Reaction
TMG	Trial Management Group
TSC	Trial Steering Committee
TMF	Trial Master File
-(z-)BZD	Benzodiazepines and z-drugs (Zoplicon and Zolpidem)

TRIAL FLOW CHART

Figure 1: Flow chart for participant's pathway

■ STUDY PROTOCOL

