3.1.4 Prescriptions for benzodiazepines

The fourth secondary objective is to compare the effect of blended care combining an interactive educational e-tool with face-to-face clinical consultations versus usual care on the number of DDD of (z-)BZD prescribed at 6, 12, 26 and 52 weeks from baseline in a population of adult primary care patients chronically using benzodiazepines for a primary indication of sleeping disorders.

Null hypothesis: blended care is not superior to usual care in terms the number of DDD of benzodiazepines prescribed at 6, 12, 26 and 52 weeks from baseline.

Alternative hypothesis: blended care will decrease the number of DDD of (z-)BZD prescribed at 6, 12, 26 and 52 weeks from baseline compared to usual care.

PICOT

Population: Patients receiving prescriptions for (z-)BZD on a daily basis in the last 6 months for a primary indication of sleeping problems aged 18 and older.

Intervention Blended care combining an interactive educational e-tool with face-to-face clinical consultations with the GP.

Comparator Care as usual for chronic (z-)BZD use left at the discretion of the GP. This may include a minimal intervention (discontinuation letter or discontinuation advice) or a more extended intervention, in combination with (z-)BZD tapering.

Outcome The number of DDD of (z-)BZD prescribed.

Time The outcome will be assessed 6, 12, 26 and 52 weeks after initiation of the intervention.

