3.5 Secondary endpoints

- The proportion of subjects with a negative benzodiazepine urine test assessed 6 months after initiation of the intervention.
- The proportion with a better score in quality of life from baseline to 6, 12, 26 and 52 weeks.

- The proportion of subjects that self-report to have ceased benzodiazepine use at 6, 12, 26 and 52 weeks.
- The number of DDD of benzodiazepines prescribed at 6, 12, 26 and 52 weeks from baseline.

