7 TRIAL PROCEDURES

7.1 Recruitment

For the recruitment of GPs, each academic centre will regionally organise training and education sessions on the management of withdrawal of (z-)BZDs and invite GPs to attend one of these. These two-hour sessions aim to refresh and train GPs' knowledge and skills on (z-)BZD discontinuation rather than to teach new information and skills.

Specifically, the training sessions will consist of an existing educational package on benzodiazepine withdrawal that was developed by the Project Group Benzodiazepines and commissioned and financed by the Federal Public Service Health. These trainings available in French and Dutch are typically delivered by a trained GP and psychologist.

The content of these sessions cover non-pharmacological minimal interventions and extended interventions and pharmacological approaches for (z-)BZD tapering and withdrawal and are based on the contents of

- “Anxiety, stress and sleeping problems. A toolbook for general practitioners” which was developed in 2005 by order of the Belgian Government as part of the fourth national campaign for a responsible use of (z-)BZD.
- The online guideline “Sleeping pill and sedatives. How to assist your patients in their search for other solutions” which was developed as part of the latest (2018) national campaign for a responsible use of (z-)BZD. Both toolboxes are available in French, Dutch.

At the end of the sessions attending GPs will be invited to participate in the study.

7.1.1 *Patient identification*

The participating GPs will be asked to recruit consecutively 10 patients consulting for benzodiazepine prescription renewal, during a period of maximum 6 weeks. This is feasible since assuming that 10% of the population takes (z-)BZDs on a regular basis –a conservative estimate- and assuming prescriptions are provided on a bi-monthly basis, full time working GPs see monthly between 50 and 150 patients for (z-)BZD prescription renewals (depending on the patient load varying between 1000 and 3000).

During this period of 6 weeks, the GP will keep a list of the number of eligible patients consulting for a BZD prescription renewal and will tally whether they were invited to participate in the study or not. In the latter case the GP will be asked to give the reason why he/she did not do so. Also when a patient declines participation in the study, the GP will ask for and record the reason of refusal.

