7.6 Baseline data

At study entry, the following baseline data will be collected for each participating patient:

- Demographics, comorbidities and medication
- Toxicological screening of urine
- Self-reported use of (z-)BZD (drug name(s), quantity)
- (z-)BZD prescriptions in last 6 months (drug name(s), quantity)
- Audit-C
- EQ5D-3L
- Benzodiazepine Dependence Self-Report Questionnaire
- Insomnia Severity Index
- HLS-EU-Q16

Except for the toxicological screening for which the procedure is explained in 7.7, data will be collected either by completion of the eCRF or via questionnaires sent to the patient.

The invitation to complete the first questionnaire will be sent after signature of the Informed Consent Form (ICF) and registration of the patient in the online platform Slaapzorgeloos/Dormir Sereinement. This first (baseline) questionnaire should thus be completed before the baseline visit takes place. By doing so, we would like to prevent that the patients' answers are influenced by the outcome of the randomisation (see section 7.3.1 *method of implementing the allocation sequence*).

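### DDD prescribed is a raw count over windows of unequal length, so visits are not on one scale and a constant effect can look like one that grows

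*Combined protocol and SAP*

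**What the plan says.** The Trial Summary counts "The number of DDD of (z-)BZD prescribed in the preceding interval assessed at week 6,12,26 and 52". Section 3.5 has "The number of DDD of benzodiazepines prescribed at 6, 12, 26 and 52 weeks from baseline", with no window. The objective in section 3.2 (subsection numbered 3.1.4) says only "The outcome will be assessed 6, 12, 26 and 52 weeks after initiation of the intervention". No section states a per-day or per-week rate, an offset for interval length, or a rule for a prescription whose supply runs past the end of a window.

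For baseline, section 7.6 collects the drugs and quantities prescribed over the previous six months. Section 7.7 leaves the timing of follow-up renewals to the GP and the patient's needs.

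Section 10.3.3 treats every secondary endpoint other than the six-month urine test as binary and longitudinal, with group, time and group-by-time terms. A significant interaction leads to visit-specific effects; otherwise one overall group effect is reported. No model for a DDD count is named.

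The only prescribing interval given is in the recruitment argument of section 7.1.1: "assuming prescriptions are provided on a bi-monthly basis, full time working GPs see monthly between 50 and 150 patients for (z-)BZD prescription renewals".

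**The concern.** A raw count rises with the length of the window it covers, even when use does not change. The last window here is more than four times as long as the first two, and only the last matches the six-month baseline in length. A time course of such counts mixes prescribing behaviour with calendar arithmetic.

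Two consequences follow. First, if the counts are compared on an additive scale, a steady effect looks like a growing one. Section 10.3.3 uses the interaction test to choose between visit-specific and overall effects, so this pattern could decide what is reported. Second, a 6-week window may be shorter than one prescription cycle. A patient who has changed nothing can then show zero DDD, and a split into zero versus any would count that patient as having stopped.

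**Working it through.** **Meaning of the two-month cycle.** Inputs from section 7.1.1: 10% regular users, patient load 1000 to 3000, and the stated 50 to 150 renewals a month. Renewals per month = load × 0.10 / cycle in months. With a two-month cycle, 1000 × 0.10 / 2 = 50 and 3000 × 0.10 / 2 = 150, which reproduces the stated range exactly. Twice-monthly prescribing would give 200 to 600. The assumed cycle is therefore 365 / 6 = 60.8 days, or 8.69 weeks.

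**Scale.** Windows under the Trial Summary wording are 6 − 0 = 6, 12 − 6 = 6, 26 − 12 = 14 and 52 − 26 = 26 weeks. Expected DDD for an unchanged user of 1 DDD/day is 7 × weeks. The 50% lower rate is illustrative.

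| Visit (week) | Window (weeks) | Unchanged user, DDD | At 50% lower rate, DDD | Difference, DDD | Ratio | Difference per day |
|---|---|---|---|---|---|---|
| 6 | 6 | 42 | 21 | 21 | 0.5 | 0.5 |
| 12 | 6 | 42 | 21 | 21 | 0.5 | 0.5 |
| 26 | 14 | 98 | 49 | 49 | 0.5 | 0.5 |
| 52 | 26 | 182 | 91 | 91 | 0.5 | 0.5 |

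The count rises 182 / 42 = 4.3-fold with no change in use. The raw difference grows in step, while the ratio and the per-day difference stay constant.

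If sections 3.2 and 3.5 mean cumulative counts from baseline, the windows are 6, 12, 26 and 52 weeks and the unchanged user scores 42, 84, 182 and 364 DDD. The windows are still unequal, but only one is shorter than 8.69 weeks.

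**Refill timing.** Assumptions: steady 1 DDD/day, one prescription per cycle of c weeks, and phase uniform at the start of the window. For a window of L weeks, let r = L/c, k = floor(r) and f = r − k. The number of prescriptions is k with probability 1 − f and k + 1 with probability f. The mean is 7L DDD, the SD is 7c√(f(1 − f)), and CV = SD / mean.

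For L = 6 and c = 8.69: r = 0.69, so 1 − 0.69 = 31% have zero and the rest have one prescription of about 61 DDD. The SD is 28 and the CV is 28 / 42 = 0.67. The documents fix no prescribing interval for follow-up, so a range is shown.

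| Cycle (weeks) | Zero DDD in a 6-week window | CV, 6 weeks | CV, 14 weeks | CV, 26 weeks |
|---|---|---|---|---|
| 4.35 (monthly) | 0% | 0.35 | 0.13 | 0.02 |
| 8 | 25% | 0.58 | 0.25 | 0.13 |
| 8.69 (two months) | 31% | 0.67 | 0.30 | 0.03 |
| 13 | 54% | 1.08 | 0.25 | 0.00 |

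The very low values at 26 weeks arise because 26 weeks is close to a whole number of cycles (26 / 8.69 = 2.99). At 8 weeks the CV is 0.13.

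**A combined 0-12 window.** At c = 8.69, r = 12 / 8.69 = 1.38, so no unchanged user has zero, and the CV is √(0.38 × 0.62) / 1.38 = 0.35. At c = 13 a share of 1 − 12/13 = 8% would still show zero.

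**The case against.** A reader might infer that the early arm comparisons are invalid, or that refill timing dominates the week-6 and week-12 results under any model. The documents do not support this, for four reasons.

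- Both arms share the same windows, and randomisation should balance refill phase. At a single visit, unequal windows distort nothing and refill timing adds noise, not bias.
- The CV of 0.67 describes one patient. With 1200 / 2 = 600 patients per arm and an SD of 28, refill timing contributes a standard error of 28 × √(2/600) = 1.6 DDD to the week-6 difference, ignoring clustering. That is about 4% of the 42-DDD mean. The documents give no between-patient variance of DDD, so dominance cannot be shown.
- The scale problem depends on the model. With a log link and categorical time, interval length cancels and the ratio is 0.5 at every visit. Section 10.3.3 names no count model, so the artefact is a risk left open and not a feature of a planned analysis.
- The two-month cycle appears only as a feasibility assumption ("assuming prescriptions are provided on a bi-monthly basis"). It is not a schedule for follow-up, and monthly prescribing would give no false zeros. Uniform phase is also an assumption: patients are recruited at a renewal, but the baseline visit may come up to 12 weeks after screening.

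All four points stand, and they limit the concern. They do not remove the unequal windows, the differing definitions, or the lack of any rate, offset or count model.

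**Conclusion.** The point holds as a scale and definition problem. Under the Trial Summary wording, an unchanged user of 1 DDD/day moves from 42 to 182 DDD, and visits cannot be compared with each other or with baseline unless window length is allowed for. On an additive scale, a constant rate effect appears as a growing one (21 to 91 DDD in the 50% illustration) and can trigger the interaction rule in section 10.3.3. In a zero-versus-any analysis, about 31% of unchanged users would count as stopped at weeks 6 and 12 and none at weeks 26 and 52, given a two-month cycle and random phase. The early figure is 25% at 8 weeks, 0% with monthly prescribing and 54% with 13-weekly prescribing.

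The unequal-window finding needs no assumption about refills and holds under either reading of the endpoint. The false-zero figures rest wholly on the assumed cycle and phase. Single-visit arm contrasts are not biased. Section 10.3.3 labels the secondary analyses hypothesis generating, so the primary result and sample size are unaffected. This is a worthwhile, low-cost improvement.

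**What to change.** Define the outcome once, in the same words, in the Trial Summary and sections 3.2 and 3.5: DDD prescribed per day over stated, non-overlapping windows. A count model with log interval length as an offset is an equivalent route. State whether a prescription issued at the baseline visit falls in the first window; under the two-month assumption this alone can move a patient from 0 to about 61 DDD.

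In section 10.3.3, name a continuous or count model for this endpoint in place of the binary one, and do not analyse it as zero versus any. Adjust for baseline DDD per day from the six-month prescription data in section 7.6. Report weeks 0-12 as one window, with week 6 kept as descriptive if wanted. A rate alone corrects the scale but leaves the refill noise of a 6-week window; the combined window reduces it. Making weeks 26-52 the main comparison is optional and not part of this fix.

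The cost is a wording change, slightly more analysis work and less emphasis on week 6. The baseline data are already planned. For follow-up, the sponsor should confirm that dates and quantities of prescriptions are captured, because the intervention list in section 7.7 names dose increases and decreases but not these.
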